#### **4.3 DOSE JUSTIFICATION FOR SUPLEXA THERAPEUTIC CELL DOSE**

The initial cumulative dose selected for this study was based entirely on preclinical mouse xenograft studies in which we dosed mice at ~28x the intended human regimen 3 clinical doses with an option to extend to 6 doses, with each dose approximately 2.5 B cells (range 1.9-3.9 B cells). Given the complete absence of treatment related adverse events for SUPLEXA in the ongoing human study, we propose that after the first 3 doses, administration of up to 14 additional treatments of 5B cells every 2 weeks will be well tolerated, and the actual number of doses depends on the SUPLEXA manufacturing yields for each of 2 patient-specific SUPLEXA batches.

The DSMB will provide an additional review of all safety data and predetermined points in the progress of the clinical study.

#### **4.4 STUDY DURATION**

##### **Study Duration**

For each subject, the study duration is expected to be as follows:

Screening:	Up to 5 weeks
Treatment:	
Minimally 3 weeks for subjects starting at recommended dose.
 
Optional additional doses will be at discretion of the investigator in agreement with Sponsor. Subjects may receive additional treatment with study intervention depending on emerging data and SUPLEXA manufacturing yield.

Follow-up:	
Every 8 weeks for up to 48 weeks from last dose of study intervention or earlier if the study is terminated by the Sponsor.
 
Beyond Week 48, subjects may be contacted every 12 weeks up to a maximum of 24 months after the last dose of SUPLEXA or earlier if the study is terminated by the Sponsor.

## 5 ELIGIBILITY CRITERIA

### 5.1 INCLUSION CRITERIA

Subjects are eligible to be included in the study only if all the relevant criteria for their cohort apply:

#### Age

1. Adult subjects at least 18 years of age at the time of signing the PICF.

#### Type of Subject and Disease Characteristics

##### Solid Tumours

2. Histologically or cytologically confirmed diagnosis of locally advanced or metastatic solid tumour.
3. Have 1 or more tumours measurable based on RECIST v1.1 as assessed by the local site Investigator. Radiographic scans should be obtained within 5 weeks of Screening. Lesions situated in a previously irradiated area are considered measurable if objective progression has been demonstrated following radiation to such lesions.
4. Subjects who did not attain a durable response after receiving at least one standard/approved therapies which may include chemotherapy, targeted agents, radio-, immuno- conjugates, check point inhibitors or where there is no approved therapy. This includes subjects who attained a long-term stable disease (SD), or partial response (PR) are eligible. Long term SD subjects on a checkpoint inhibitor may continue checkpoint inhibitor (CPI) therapy.  
\* Any therapies defined as immunosuppressive require a washout period of at least 4 weeks, defined as 4 weeks (28 days) prior to blood collection for SUPLEXA manufacturing and any SUPLEXA dose administration.

##### Haematologic malignancies

5. Histologically or cytologically confirmed multiple myeloma, lymphoma, and chronic lymphocytic leukemia (collectively termed as haematologic malignancies for the purposes of this protocol) which has relapsed or is refractory advanced malignancy for which no curative standard therapy exists.

#### Pregnancy and Contraception

Contraception use by men or women should be consistent with local regulations regarding the methods of contraception for those participating in clinical studies. Please also refer to Appendix 4 (Section 10.4) for more information.

6. Women of childbearing potential must have a negative serum or urine pregnancy test within 72 hours prior to receiving the first study intervention administration. If the urine test is positive or cannot be confirmed as negative, a serum pregnancy test will be required.

7. For women of childbearing potential who are not abstinent and intend to be sexually active with a non-sterilized male partner, must be willing to use an adequate method of contraception from 4 weeks prior to the first study intervention administration and 60 days following last day study intervention administration and agrees not to donate eggs (ova, oocytes) for the purpose of reproduction during this period as it is unknown how activated SUPLEXA may impact a pregnancy. Acceptable methods include hormonal contraception (oral contraceptives – if on stable dose, patch, implant, and injection), intrauterine devices, or double barrier methods (e.g., vaginal diaphragm/ vaginal sponge plus condom, or condom plus spermicidal jelly), sexual abstinence or a vasectomized partner. Women may be surgically sterile or at least 1-year post-last menstrual period. *Note: Abstinence is acceptable if this is the usual lifestyle and preferred contraception for the subjects.*
8. Male subjects must be surgically sterile or must agree to use adequate method of contraception during the study and at least 90 days following the last day of study intervention administration. Male subjects should also refrain from sperm donation during this time.

*Note: Abstinence is acceptable if this is the usual lifestyle and preferred contraception for the subjects.*

### **Informed Consent**

9. Capable of giving signed PICF. The subject (or legally acceptable representative if applicable) provides written informed consent for the study which includes compliance with the requirements and restrictions listed in the PICF and in this protocol.

### **5.2 EXCLUSION CRITERIA**

The subjects must be excluded from participating in the study if they meet any of the following:

#### **Medical Conditions**

1. Known central nervous system (CNS) metastases and/or carcinomatous meningitis.
2. Prior allogeneic transplant.
3. Diagnosis of immunodeficiency or is receiving chronic and non-physiological, systemic steroid therapy or any other form of immunosuppressive therapy.
4. Active uncontrolled bacterial, viral, or fungal infection requiring systemic therapy at screening or Day 1.
5. History or current evidence of any condition, therapy, or laboratory abnormality that might confound the results of the study, interfere with the subject's participation for the full duration of the study, or is not in the best interest of the subject to participate, in the opinion of the treating Investigator.
6. Any unresolved Grade 2 or greater reversible toxicity from a previous anticancer therapy except for alopecia or Grade 2 neuropathy.
7. Clinically significant cardiovascular disease, including any of the following:

- a. Stroke or myocardial infarction within 6 months prior to first dose in the study.
- b. Presence of unstable angina within 6 months prior to first dose in the study.
- c. Congestive heart failure of New York Heart Association Grade 2 or higher.
- d. History or presence of clinically significant ventricular arrhythmias, or conduction abnormality; presence of clinically significant atrial fibrillation and resting bradycardia.
- e. Corrected QT interval (QTcF) of  $>450$  msec (males) or  $>470$  msec (females) using Fridericia's correction formula.
- f. History of congenital long QT syndrome.

8. Known history of testing positive for human immunodeficiency virus (HIV), and/or positive test for Hepatitis B virus surface antigen (HBsAg) and/or positive Hep C antibody result with detectable hepatitis C virus (HCV) ribonucleic acid (RNA) indicating acute or chronic infection.

*Note: Subjects who have been vaccinated against Hepatitis B and hence are positive only for the Hepatitis B surface antibody are permitted to participate in the study.*

9. A serious non-malignant disease (e.g., psychiatric, substance abuse, uncontrolled intercurrent illness, etc.) that could compromise protocol objectives in the opinion of the Investigator and/or the Sponsor.

10. At high risk of developing TLS per ([Cairo, 2010](#)). Specifically:

- a) Burkitt's lymphoma
- b) ALL with LDH  $\geq 2 \times \text{ULN}$  or WBC  $\geq 100 \times 10^9$  per  $\mu\text{L}$ .
- c) AML with WBC  $\geq 100 \times 10^9$  per  $\mu\text{L}$ .

11. Any other condition that, in the opinion of the Investigator, would prohibit the subject from effectively participating in the study.

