### 6.8.1 Prophylaxis

For cytotoxic chemotherapies, allopurinol administration is recommended 24 hours prior to initiation of treatment with SUPLEXA because of the immediate action of the cytotoxic chemotherapy. For cellular therapies however, cells require at least a day to migrate out of the circulation to the tumour bed and synchronous tumour lysis will be delayed. Therefore, allopurinol will be administered concomitantly with each SUPLEXA dose, and between doses as directed by the investigator.

The following pretreatment regimen is suggested, although a different regimen based on local standard of care/ institutional practices is permitted: Approximately 1 hour (60 min  $\pm$  15 min) before each SUPLEXA infusion, all subjects will receive single administration of:

- Acetaminophen 1000 mg PO (for potential fever)
- Diphenhydramine 12.5 mg PO (for potential rash)
- Allopurinol 100 mg (IV or PO) (for potential tumour lysis syndrome in subjects who are at intermediate risk for TLS; refer to [Figure 6](#)). This should be followed, unless the investigator determines continued oral dosing of allopurinol is required.

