## 9 STATISTICAL CONSIDERATION

### 9.1 SAMPLE SIZE DETERMINATION

Approximately 60 subjects will be enroled with a cap of about 8 subjects per individual tumour type (e.g., melanoma, breast, prostate, lung, haematological malignancies, etc.). If promising anti-tumour activity coupled with acceptable safety is observed, overall sample size and/or cap per tumour type may be expanded.

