## 10.8 APPENDIX 8: TLS TOXICITY MANAGEMENT

**Note these are guidelines that might require modification based on clinical circumstances of each subject and consider institutional standard of care treatment protocols, and failure to exactly follow these guidelines is not a protocol deviation or violation as follows:**

Tumor lysis syndrome (TLS) is an oncology emergency that occurs as a result of rapid tumor cell breakdown and the consequent release of massive amounts of intracellular contents, including potassium, phosphate, and uric acid, into the systemic circulation. These metabolic disturbances lead to life-threatening conditions and may cause sudden death if not treated. TLS commonly occurs following initiation of cytotoxic treatment in patients with high-grade lymphomas or acute lymphoblastic leukemia. Spontaneous cases involving both solid and hematologic tumors have also been reported. Rarely, TLS occurs following treatment with irradiation, corticosteroids, hormonal therapy, or biologic therapy. It is necessary to identify subjects at risk for TLS early in order to initiate preventive measures. In the event that preventive measures fail, the clinical parameters and signs of TLS must be understood and recognized so that treatment can begin as soon as possible, as this condition is a significant cause of morbidity and mortality.

When tumor cells are rapidly broken down and their contents released into the extracellular space, the released ions and compounds can cause metabolic disturbances too great to be neutralized by the body's normal mechanisms. The syndrome characterized by these metabolic derangements is known as TLS. TLS can cause life-threatening conditions and even death unless appropriately and immediately treated.

[figure not shown]
The Cairo-Bishop definition provided specific laboratory criteria for the diagnosis of TLS, as well as a grading system for describing the degree of severity of TLS ([Cairo, 2010](#)). Laboratory TLS is defined as any two (or more) of the following abnormalities:

- Serum uric acid level  $\geq 8$  mg/dL, or 25% increase from baseline.
- Serum potassium level  $\geq 6$  mmol/L, or 25% increase from baseline.
- Serum phosphate level  $\geq 6.5$  mg/dL in children and  $\geq 4.5$  mg/dL in adults, or 25% increase from baseline.
- Serum calcium level  $\leq 7$  mg/dL, or 25% decrease from baseline.

All these abnormalities must occur within 7 days after the dosing with SUPLEXA.

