**Figure 6: TLS risk assessment of solid tumours, myelomas and chronic leukaemias**

\*Bulky, solid tumours, sensitive to chemotherapy, such as neuroblastomas, germ-cell tumours and small-cell lung cancer are

Source: (Cairo, 2010)

Abbreviation: LRD, low risk disease; IRD, intermediate risk disease

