**Table 10: Recommendation for Prevention and Treatment of Tumour Lysis Syndrome**

Risk Level	Low-risk disease	Intermediate-risk disease	High-risk disease
Diagnostic measures	
 
No specific measures
 
	
 
Daily monitoring of laboratory abnormalities before and during the first 7 days of anticancer therapy
 
	
 
At least twice daily monitoring of laboratory abnormalities before and during the first 7 days of anticancer therapy
 

Preventive measures	
 
Moderate hydration is recommended
 
	
 
Vigorous hydration
 
Keep urinary output >100 mL/h
 
Treatment with allopurinol or febuxostat should be started at least 24 hours before initiation of anticancer therapy and should be continued till normalization of uric acid levels and signs of large tumour burden are absent
 
	
 
vigorous hydration
 
Keep urinary output >100 mL/h
 
Single dose 6 mg of rasburicase. Repeat doses, as necessary. in case of contraindication treatment with febuxostat
 

Treatment of established tumour lysis syndrome	
 
Admission to intensive care unit with continuous cardiac monitoring and monitoring of laboratory abnormalities every 4–6 hours
 
early nephrology consultation to estimate the indications for renal replacement therapy
 
Correction of electrolyte abnormalities
 
vigorous hydration, keep urinary output >100 mL/h
 
Single dose 6 mg of rasburicase. Repeat doses as necessary. In case of contraindication, treatment with febuxostat
 
		

 Source: [\(Alakel, 2017\)](#)

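### The tumour lysis safeguards are not matched to the diseases that can enrol: two of three items in exclusion 10 can exclude nobody, no visible text classes non-Burkitt lymphoma, and the allopurinol timings disagree

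*Combined protocol and SAP*

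**What the plan says.** **Who can enter.** Section 5.1, inclusion 5, defines the haematologic cohort as "Histologically or cytologically confirmed multiple myeloma, lymphoma, and chronic lymphocytic leukemia", relapsed or refractory. The other cohort requires a solid tumour.

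**Who is excluded for TLS risk.** Section 5.2, item 10, covers subjects "At high risk of developing TLS per" a cited consensus. The word *Specifically* then limits it to (a) "Burkitt's lymphoma", (b) ALL above an LDH or white-cell limit, and (c) AML above a white-cell limit. The white-cell limit in both (b) and (c) is 100 x 10^9 per microlitre.

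**How TLS risk is graded.** Section 10.8 (Appendix 8) applies Table 10 by the risk level in Figure 6. Section 6.8.1 also points to Figure 6 to identify the intermediate-risk subjects who receive allopurinol. The figure is titled "TLS risk assessment of solid tumours, myelomas and chronic leukaemias". Its content is not in the text available for review. Appendix 8 also states: "TLS commonly occurs following initiation of cytotoxic treatment in patients with high-grade lymphomas or acute lymphoblastic leukemia".

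**When allopurinol is given.** Section 6.8.1 says: "Therefore, allopurinol will be administered concomitantly with each SUPLEXA dose, and between doses as directed by the investigator". Its suggested regimen puts the dose 60 ± 15 minutes before each infusion. The Schedule of Activities note gives 60 ± 20 minutes and refers the site to both 6.8.1 and 10.8. For intermediate risk, Table 10 says: "Treatment with allopurinol or febuxostat should be started at least 24 hours before initiation of anticancer therapy".

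**The concern.** The amendment history records that item 10 was added as a safety precaution, and Section 5.2 makes it binding. An exclusion aimed mainly at diseases that cannot enrol gives little of that protection. Table 1 bases the TLS risk on cell therapy for haematologic malignancies and considers TLS less likely in solid tumours, so the haematologic cohort is where the safeguard matters most.

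The risk level also has consequences. In Table 10, low risk carries no specific diagnostic measures. Intermediate risk carries daily laboratory monitoring before and during the first 7 days, vigorous hydration and uric-acid treatment. A site that cannot tell which column applies to a lymphoma subject, or that finds two allopurinol timings for the same subject, will improvise. TLS management would then vary between sites in a first-in-human trial whose primary endpoints are safety endpoints.

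**Working it through.** No sample-size, power or error-rate figure is involved. The check sets the passages side by side, with a unit conversion and a comparison of time windows.

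**1. Exclusion 10 against inclusion 5**

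| Item 10 category | Disease admitted? | Can it exclude anyone? |
|---|---|---|
| (a) Burkitt's lymphoma | Yes, as a lymphoma | Yes |
| (b) ALL with LDH or white-cell limit | No | No |
| (c) AML with white-cell limit | No | No |

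Two of three categories are inert.

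**2. The white-cell limit as printed**

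- Conversion: 100 x 10^9 per microlitre x 10^6 microlitres per litre = 10^17 per litre.
- Physical check: 1 microlitre = 10^9 cubic micrometres. 10^9 / 10^11 cells = 0.01 cubic micrometre per cell, even if the sample were nothing but cells. No sample can reach the limit.
- Assumption, since the documents do not state the intent: if the litre was meant, as in the platelet row of exclusion 13, the limit would be 100 x 10^9 per litre = 100,000 per microlitre, lower than printed by a factor of 10^6.
- The limit appears only in (b) and (c), which step 1 shows to be inert. The error changes no subject's eligibility.

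**3. Which enrolled diseases have a visible TLS class**

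- Solid tumours and myeloma: named in the Figure 6 title.
- Chronic lymphocytic leukaemia: falls under chronic leukaemias in the title.
- Burkitt's lymphoma: high risk and excluded by item 10(a).
- Other lymphoma: not named in the title, and not classed in item 10, Section 6.8.1, Table 10 or elsewhere in the visible text. The figure's abbreviation list gives low-risk and intermediate-risk disease only.

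Section 9.1 bounds the number affected: "Approximately 60 subjects will be enroled with a cap of about 8 subjects per individual tumour type". Whether haematologic malignancies count as one type or lymphoma counts alone, lymphoma contributes at most about 8 subjects (8/60 = 13%). This assumes that lymphoma subtypes are not counted separately and the cap is not raised, which the section allows.

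**4. Allopurinol lead time, intermediate risk**

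| Source | Lead time before treatment |
|---|---|
| Section 6.8.1 | 60 ± 15 = 45 to 75 min |
| Schedule of Activities | 60 ± 20 = 40 to 80 min |
| Table 10 | 24 x 60 = 1,440 min or more |

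The first two overlap but differ. Neither overlaps the third: 1,440 / 80 = 18, and 1,440 - 80 = 1,360 min, or 22 h 40 min between the nearest limits.

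**5. Batch 2 (a point to check only)**

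Section 6.8.1 attaches premedication to every infusion. In the extracted Schedule of Activities the prophylaxis row shows three marks and the SUPLEXA administration row four. The extraction is visibly broken at this place, so the count is not evidence of an omission.

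**The case against.** The best defence is that most of this is advisory and partly explained.

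- **Timing.** Section 6.8.1 cites the 24-hour practice for cytotoxic chemotherapy, argues that lysis is delayed with cells, and concludes that dosing with the infusion is acceptable. Its regimen is a suggestion, with local practice allowed. Appendix 8 says that departing from it does not count as a deviation. A reader might infer that sites face two rules they cannot both obey; the documents do not support that, because neither is binding. What stands is that Table 10 was not adapted, does not refer back to 6.8.1, and is cited beside it in the Schedule of Activities.
- **Lymphoma.** A reader might infer that lymphoma subjects have no TLS class. That goes too far: Burkitt's is classed, and Figure 6 cannot be seen. Its absence from the review text is not a fault of the plan. Appendix 8 also ties the high-grade lymphoma remark to cytotoxic treatment and calls TLS after biologic therapy rare. What stands is that no visible passage classes non-Burkitt lymphoma.
- **Other protection.** Exclusions 5 and 11 give the investigator discretion, predose chemistry includes the TLS analytes, and TLS parameters inform treatment extension. These reduce the risk but do not repair item 10.
- **Study hold.** A reader might infer that one related Grade 3 TLS case suspends the trial. Under that criterion Section 7.1 requires at least 3 related cases of Grade 3 or higher among immunological events, CRS and TLS.

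**Conclusion.** The point holds as a set of passages to reconcile. Two of the three categories in a binding exclusion concern diseases the trial does not admit, which is certain from the text. The printed white-cell limit is impossible, also certain, but affects no eligible subject. The absence of a class for non-Burkitt lymphoma rests on the title and abbreviation list of a figure not seen, so it is a statement about the visible text only; under the current cap it would concern at most about 8 of about 60 subjects. The allopurinol timings do not overlap (at most 80 minutes against at least 1,440), softened by the reason in 6.8.1 and the advisory status of both texts. The batch 2 question is unproven. Nothing here alters the sample size or any planned analysis.

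**What to change.** The sponsor's clinicians should:

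1. Reconcile exclusion 10 with the diseases that inclusion 5 admits, and confirm the intended white-cell unit if (b) and (c) are kept.
2. Confirm that Figure 6 covers lymphoma other than Burkitt's, or state where those subjects are classed.
3. Reconcile Section 6.8.1, the Schedule of Activities note and Table 10 on when allopurinol starts, including the ± 15 and ± 20 minute windows, and make each refer to the others.
4. Check in the source document whether the prophylaxis row of the Schedule of Activities is meant to cover batch 2 infusions.

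The eligibility content, unit and timing are theirs to decide; none is proposed here. The cost is an amendment to wording and possibly one figure or cross-reference. Any effect on screen failures depends on what they decide for item 10.

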### Diagnostic Assessments

12. A performance status  $\geq 2$  on the Eastern Cooperative Oncology Group (ECOG) Performance Scale (solid tumours cohort) or Karnofsky performance scale of  $\geq 60$  (haematologic malignancies cohort)

13. Does not demonstrate adequate organ function as defined as an excursion beyond the acceptable limits below. All screening laboratories should be performed at screening and on the day of first administration of study therapy.

System	Laboratory Value
Haematological	
Absolute neutrophil count (ANC)	$\leq 50\%$ lower limit of normal (LLN)
Lymphocyte (WBC)	$\leq 50\%$ LLN
Platelets	$<100 \times 10^9/\text{L}$
Haemoglobin	$\leq 9 \text{ g/dL}$ or, $\leq 5.6 \text{ mmol/L}^*$
Renal	

Creatinine OR	>1.5 times upper limit of normal (ULN) OR
Measured or calculated**creatinine clearance (CrCl) Glomerular filtration rate (GFR) can also be used instead of creatinine or CrCl	< 45 mL/min for subject with creatinine levels
Hepatic	
Total bilirubin	> 1.5 × ULN OR direct bilirubin ≥ULN for subjects with total bilirubin levels > 1.5× ULN
Aspartate aminotransferase (AST) and alanine aminotransferase (ALT)	>2.5 × ULN (> 5 × ULN for subjects with liver metastases)

\* Criteria must be met without erythropoietin dependency and without packed red blood cell (pRBC) transfusion within last 2 weeks

\*\* Creatinine clearance should be calculated per institutional standard.

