#### Karnofsky Performance Status (Haematologic malignancies Cohort)

Karnofsky performance status scale will be performed at screening to assess subject's functional impairment, ranging from 100 to 0, in increments of 10, where 100 is normal health and 0 is death ([Table 3](#)). To be eligible to participate in this study, subjects must have a Karnofsky performance status of  $\geq 60\%$ . This scale was shown to be valid in assessing geriatric population ([Crooks, 1991](#)).

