**Table 3: Karnofsky Performance Status**

Able to carry on normal activity and to work; no special care needed.	100	Normal; no complaints; no evidence of disease.
	90	Able to carry on normal activity; minor signs or symptoms of disease.
	80	Normal activity with effort; some signs or symptoms of disease.
Unable to work; able to live at home and care for most personal needs; varying amount of assistance needed.	70	Cares for self; unable to carry on normal activity or to do active work.
	60	Requires occasional assistance but is able to care for most of their personal needs.
	50	Requires considerable assistance and frequent medical care.
Unable to care for self; requires equivalent of institutional or hospital care; disease may be progressing rapidly.	40	Disabled; requires special care and assistance.
	30	Severely disabled; hospital admission is indicated although death not imminent.
	20	Very sick; hospital admission necessary; active supportive treatment necessary.
	10	Moribund; fatal processes progressing rapidly.
	0	Dead

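### Exclusion criterion 12 bars haematologic subjects with Karnofsky 60 or more, the very subjects Section 8.2.5 requires, so no one in that cohort can satisfy both

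*Combined protocol and SAP*

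**What the plan says.** Section 5.2 opens with the rule that governs every item beneath it: "The subjects must be excluded from participating in the study if they meet any of the following". Meeting one item is enough to exclude.

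Item 12, under Diagnostic Assessments, covers performance status in both cohorts. Its first half excludes a score of 2 or more "on the Eastern Cooperative Oncology Group (ECOG) Performance Scale (solid tumours cohort"). Its second half continues "or Karnofsky performance scale of" and gives the cut-off, in the markup of the text, as "\geq 60$ (haematologic malignancies cohort"), that is, 60 or more.

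Section 8.2.5 describes the Karnofsky scale as "ranging from 100 to 0, in increments of 10, where 100 is normal health and 0 is death". It then states the entry rule for the haematologic cohort: "To be eligible to participate in this study, subjects must have a Karnofsky performance status of" 60% or more.

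The inclusion criteria in Section 5.1 give no performance-status threshold. The Schedule of Activities says only that ECOG is used for solid tumours and Karnofsky for haematologic malignancies. Item 12 is therefore the only performance-status rule in the eligibility section, and Section 8.2.5 is the only other place that states a Karnofsky cut-off.

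**The concern.** The same scale, cohort, sign and cut-off appear once as a reason to exclude and once as a requirement for entry. The two scales in item 12 run in opposite directions: a higher ECOG grade is worse function (Table 2), while a higher Karnofsky score is better function (Table 3). An at-or-above cut-off is the natural form of an exclusion for ECOG. Applied to Karnofsky, it excludes the wrong end of the scale.

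Two things are at stake.

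- **Deviations.** Section 8 allows no waivers or exemptions and requires screening to confirm all eligibility criteria. A haematologic subject enrolled under Section 8.2.5 breaches item 12. Section 10.1.1.4 requires deviations to be documented and included in the study report.
- **Who is exposed.** A site that builds its checklist from Section 5.2 alone would refuse subjects in normal health and accept only those at Karnofsky 50 or lower. This is one of only two cohorts in a first-in-human study, and Section 4.1.2.1 holds back dosing of later subjects until the DSMB has cleared the cohort's first 3. If those subjects were selected by a reversed rule, the early safety picture would describe a population that Section 8.2.5 says should not be in the trial.

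**Working it through.** No sample size, power or error-rate figure is involved, so the check compares two sets of scale levels.

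**Inputs**

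- Scale: 0 to 100 in steps of 10, giving 100/10 + 1 = 11 levels; higher is better (Section 8.2.5, Table 3).
- Section 5.2: meeting any item excludes.
- Item 12, haematologic half: Karnofsky of 60 or more is an exclusion.
- Section 8.2.5: Karnofsky of 60 or more is required.

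**Sets**

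| Rule | Levels | Count |
|---|---|---|
| Excluded by item 12 | 60, 70, 80, 90, 100 | 5 |
| Left in by item 12 | 0, 10, 20, 30, 40, 50 | 6 |
| Required by Section 8.2.5 | 60, 70, 80, 90, 100 | 5 |
| Left in by item 12 **and** required by Section 8.2.5 | none | 0 |

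The first and third rows are identical: item 12 excludes exactly the set that Section 8.2.5 requires. The intersection of {below 60} and {60 or more} is empty, so 0 of 11 levels qualify under both. Level 0 means death and is only nominal; without it the result is 0 of 10 living levels.

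**Meaning of the boundary.** The highest level that item 12 lets in is 50, which Table 3 describes as "Requires considerable assistance and frequent medical care". The top level that it shuts out, 100, is a subject with no complaints and no evidence of disease.

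**Direction check within item 12.** The ECOG half excludes grades 2 and above and leaves 0 and 1, the fully active and the ambulatory with light work. That half excludes worse function, as an exclusion should. Only the Karnofsky half excludes better function.

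**With the sign reversed.** If item 12 excluded Karnofsky below 60, it would remove 0 to 50 and leave 60 to 100. That is the set in Section 8.2.5, and the contradiction would be gone.

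**Other explanations considered.** Both passages are complete, with the sign printed, so lost or redacted text does not explain the conflict. Both are in the current body of the protocol and not in the amendment history. Nothing in Section 5.1 or the Schedule of Activities overrides either one.

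**The case against.** The contradiction itself is hard to dispute. The case on the other side concerns its consequences.

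First, item 12 is not the only gate. Exclusion 5 (participation not in the subject's interest, or unlikely to be completed), 11 (any condition preventing effective participation), 13 (organ function) and 18 (life expectancy under 6 months) would remove many subjects with low scores. Wholesale entry of severely disabled subjects is therefore unlikely. This stands as a limit on the practical harm. It does not remove the contradiction: these items only narrow the pool further, and anyone who passes item 12 as printed still has a score of 50 or lower.

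Second, the intended meaning can be recovered. The ECOG half, the scale description and the sentence in Section 8.2.5 all point the same way, and an investigator would be expected to query a rule that rejects a subject in normal health. That is probably true. It makes the deviation and audit problem more likely than harmful enrolment, but it leaves the operative eligibility text wrong and dependent on each site noticing.

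Third, the analyses do not depend on item 12. The Safety Analysis Set in Section 9.2 is everyone who receives at least one dose, and the haematologic analysis in Section 9.3.2 is descriptive. This also stands: no sample size, error rate or endpoint definition changes. Damage to the cohort's results arises only if sites applied item 12 literally and so changed who entered. The documents do not show that any haematologic subject was wrongly admitted or refused.

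Fourth, it can be said that a reviewer should not choose the cut-off. The number 60 is the protocol's own in both places; only its direction in item 12 is in question, and the sponsor should confirm it.

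**Conclusion.** The concern holds. Item 12 of Section 5.2 and the eligibility statement in Section 8.2.5 cannot both be met by any haematologic subject: 0 of 11 Karnofsky levels satisfy both. That figure measures the logical overlap between the rules, not any observed effect on enrolment.

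The conclusion rests on reading Section 5.2 as an any-item exclusion list and on the direction of the scale, both of which the protocol states outright. That the cause is a reversed sign is an inference from the ECOG half of item 12 and from Section 8.2.5, though a strong one. The safety consequence and any effect on the cohort's results depend on sites having followed Section 5.2 literally, which the documents do not reveal.

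This must be fixed, because it is an operative entry rule for one of two cohorts. The study was also already under way: Section 2.3.1 reports more than 15 subjects enrolled by 19 September 2022, without saying how many were haematologic.

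**What to change.** Reconcile Section 5.2 item 12 with Section 8.2.5, with the sponsor confirming the intended direction. The change that uses only the protocol's own cut-off is to make the haematologic half of item 12 the complement of Section 8.2.5, so that it excludes Karnofsky below 60. Leave the ECOG half as it is.

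Alongside the text change:

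- Check that the eligibility checklist and the eCRF edit check carry the confirmed direction. These are not among the documents, and they may already be right.
- Check the recorded Karnofsky scores of haematologic subjects already screened or enrolled, and decide how any discrepancy from item 12 as printed will be classified in the study report.

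The cost is one symbol in the next amendment plus a short check of the checklist, the edit check and existing screening records. No sample size or analysis changes.
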